APPENDIX D SURGICAL OUTCOME CLASSIFICATIONS

The two surgery outcome classifications used in this study, the Engel system²⁰ and ILAE system,²¹ are presented in Table 7 and Table 8.

The occurrence of early postoperative seizures or auras in the first week after epilepsy surgery is relatively common and may result from the effects of the acute surgical injury (termed “neighborhood” seizures). As such, both the Engel class I and the ILAE class 1 exclude “early” seizures. The Engel classification is not specific for the exact time period (first few weeks postoperative), whereas the ILAE classification excludes seizures in the first 4 weeks. *For the purposes of this study, seizures occurring in the first 4 weeks postoperative will be excluded when evaluating both the Engel and ILAE classes.*

An additional ILAE classification, 1a, is available for those that have been seizure- and aura-free since surgery (as recommended by Wieser et al).

Table 7: Engel Surgical Outcome Classification

Class I: Free of disabling seizures
A: completely seizure-free since surgery
B: non-disabling simple partial seizures only since surgery
C: some disabling seizures after surgery, but free of disabling seizures for at least 2 years
Class II: Rare disabling seizures ("almost seizure-free")
A: initially free of disabling seizures but has rare seizures now
B: rare disabling seizures since surgery
C: more than rare disabling seizures since surgery, but rare seizures for the last 2 years
D: nocturnal seizures only
Class III: Worthwhile improvement
A: worthwhile seizure reduction
B: prolonged seizure-free intervals amounting to greater than half the follow-up period, but not < 2 years
Class IV: No worthwhile improvement
A: significant seizure reduction
B: no appreciable change
C: seizures worse

²⁰ Engel J Jr, Van Ness PC, Rasmussen TB, Ojemann LM. Outcome with respect to epileptic seizures. In: Engel J Jr, editor. *Surgical treatment of the epilepsies*. New York: Raven Press; 1993:609-21.

²¹ Wieser HG, Blume WT, Fish D, Goldensohn E, Hufnagel A, King D, et al. ILAE Commission Report. Proposal for a new classification of outcome with respect to epileptic seizures following epilepsy surgery. *Epilepsia* 2001;42:282-6.

Table 8: ILAE Surgical Outcome Classification

Class 1: Completely seizure-free; no auras

Class 1a: Completely seizure- and aura-free since surgery

Class 2: Only auras¹; no other seizures

Class 3: One to three seizure days² per year; ± auras

Class 4: Four seizure days per year to 50% reduction of baseline seizure days³; ± auras

Class 5: Less than 50% reduction of baseline seizures days to 100% increase of baseline seizure days; ± auras

Class 6: More than 100% increase in baseline seizure days; ± auras

¹ Auras are only counted if they are short in duration and similar or identical to the preoperative auras.

² A "seizure day" (for the purposes of this classification) is defined as a 24-hour period with one or more seizures. This may include an episode of status epilepticus.

³ The number of "baseline seizure days" is calculated by determining the seizure-day frequency during the 12 months before surgery, with corrections for the effects of AED reduction during diagnostic evaluations prior to the index procedure.

The purpose of this Statistical Analysis Plan (SAP) is to document analyses that are planned for the FLARE study before they are performed (*pre-specified analyses*). The results of the analyses documented here are to be presented in the clinical study final report. Selected analyses may also be presented in interim reports, DSMB reports, and manuscripts reporting study results, as deemed appropriate by the authors. Additional analyses of the study data beyond the analyses pre-specified in this plan are expected, therefore the Statistical Analysis Plan does not preclude ad hoc analyses that may provide additional useful description of the performance of the investigational device.

2 Scope

This SAP should be read in conjunction with the Clinical Study Protocol (CL10054) and Case Report Forms (MON-CRF-1001 through MON-CRF-1030). Changes to the versions of the Clinical Study Protocol (protocol) and Case Report Forms (CRFs) cited above may necessitate updates to the SAP.

3 Applicable Documents

Document Number	Document Title
CL10054	Monteris FLARE Clinical Study Protocol, Rev A
MON-CRF-1001 through MON-CRF-1030	Monteris FLARE Study Case Report Forms
NAMSA STATSOP-002	Statistics Standard Operating Procedure – Statistical Analysis Plan

4 Software

Statistical analyses, tables, listings, and figures will be primarily produced using SAS statistical software (SAS Institute, Cary, NC), version 9.2 or later, or another validated statistical software package.

5 Abbreviations

The following is a list of abbreviations used in the body of this document.

ADE	adverse device effect
AE	adverse event
AED	antiepileptic drug
BVMT-R	Brief Visual Memory Test – Revised
BNT-60	Boston Naming Test – 60 item version
CEC	Clinical Events Committee
DSMB	Data Safety and Monitoring Board
CRF	case report form
ICF	informed consent form
ICH	International Conference on Harmonization
IDE	Investigational Device Exemption
IQ	intelligence quotient
ILAE	International League Against Epilepsy
LITT	laser interstitial thermal therapy
MRI	magnetic resonance imaging

MTLE	mesial temporal lobe epilepsy
NBS	NeuroBlate® System
QOLIE-31	Quality of Life in Epilepsy – 31 item version
RAVLT	Rey Auditory Verbal Learning Test
SAE	serious adverse event
SOP	standard operating procedures
UADE	unanticipated adverse device effect
USADE	unanticipated serious adverse device effect
VAS	visual analog scale
WAIS-IV	Wechsler Adult Intelligence Scale-IV
WMS-IV	Wechsler Memory Scale-IV

6 Design

The FLARE study is a multicenter, open-label, prospective feasibility study to characterize the performance of laser interstitial thermal therapy (LITT) ablation using Monteris NeuroBlate® System (NBS) for the treatment of drug refractory mesial temporal lobe epilepsy in subjects who are candidates for surgical resection.

The study design is outlined in Figure 1.

[figure not shown]

Figure 1: Study Design Schema

7 Endpoints

The primary endpoint for the study is:

- To characterize safety (adverse events and neuropsychological changes) of LITT for the treatment of drug-refractory medial temporal lobe epilepsy

The secondary endpoints for the study are:

- To characterize seizure outcome (based on seizure frequency and surgical outcome classifications) of study subjects treated with LITT
- To characterize the quality of life of study subjects treated with LITT

8 Data Collection

Table 1 outlines the visits, visit windows, and testing requirements at each evaluation time point from Baseline through the Month 12 visit. Table 2 outlines the visits, visit windows, and testing requirements at each evaluation time point from the Month 13 visit through the Month 24 visit.

The remainder of the page is intentionally blank.

Table 1: Visits and Testing Requirements and Data Collection Summary (Baseline through Month 12)

Visit Window	Pre-Procedure				LITT Proc.	DC	Post-Procedure											
	Week -12	Week -8	Week -4	Week 0			Day 14	Mo. 1	Mo. 2	Mo. 3	Mo. 4	Mo. 5	Mo. 6	Mo. 7	Mo. 8	Mo. 9	Mo. 10	Mo. 11
	Within 7 days of enrollment	± 7 days	± 7 days	± 7 days	Within 30 days of Week 0	Day of DC	± 4 days	± 4 days	± 7 days									
Visit Type																		
Inclusion and exclusion criteria	✓																	
Informed consent	✓																	
Demographics	✓																	
Medical, surgical & epilepsy history	✓																	
QOLIE-31	✓														✓			✓
Medication review (epilepsy and non-epilepsy)	✓	✓	✓	✓	✓	✓	✓	✓	✓	✓	✓	✓	✓	✓	✓	✓	✓	✓
Physical exam	✓						✓	✓						✓				✓
Neurological exam	✓						✓	✓	✓	✓			✓	✓	✓			✓
Formal visual field testing	✓													✓				
Serum pregnancy test (if female of child-bearing potential)	✓			✓														
Neuropsychological testing ¹	✓ ²		✓ ²									✓		✓				✓
Functional assessment	✓			✓			✓	✓	✓				✓		✓	✓		✓
Seizure classification assessment	I											U		U				U
Seizure diary	D	C/D	C/D	C		D	C/D	C/D	C	C/D	C	C	C/D	C	C	C/D	C	C/D
Adverse event monitoring		✓	✓	✓	✓	✓	✓	✓	✓	✓	✓	✓	✓	✓	✓	✓	✓	✓
Treatment criteria			✓															
LITT Treatment				✓														
MRI					✓	✓								✓				
Surgical pain VAS						✓	✓											
Surgical outcome classifications ³										✓		✓		✓				✓
Subject satisfaction												✓						✓

Abbreviations: C; collect; D; dispense; DC; discharge; I; initial; LITT; laser interstitial thermal therapy; Mo.; month; MRI; magnetic resonance imaging; QOLIE-31; Quality of Life in Epilepsy - 31; U; update; VAS; visual analog scale.

¹ See Appendix A for details of the neuropsychological testing at each visit. These can be performed on a separate day than the study visit, as long as it is completed within the study window.

² Prior neuropsychological testing may be used for baseline values if the testing was conducted within 6 months prior to the specific baseline visit and there were no significant changes to the subject's AEDs or changes to the subject's clinical condition that may affect cognitive function.

³ See Appendix B for details about the Engel and ILAE surgical outcome classifications.

Table 2: Visits and Testing Requirements and Data Collection Summary (Month 13 through Month 24)

	Months 13, 14, 15, 16, & 17	Month 18	Months 19, 20, 21, 22, & 23	Month 24	Early Withdrawal
Visit Window	± 7 days	± 14 days	± 7 days	± 14 days	
Visit Type					
QOLIE-31		✓		✓	✓
Medication review (epilepsy and non-epilepsy)	✓	✓	✓	✓	
Neurological exam		✓		✓	✓
Functional assessment		✓		✓	✓
Seizure diary	C/D	C/D	C/D	C	
Adverse event monitoring	✓	✓	✓	✓	✓
Surgical outcome classifications ¹		✓		✓	✓
Subject satisfaction		✓		✓	✓
Neuropsychological testing ²					✓

Abbreviations: C; collect; D, dispense; QOLIE-31, Quality of Life in Epilepsy - 31; U, update.
¹ See Appendix B for details about the Engel and ILAE surgical outcome classifications.
² See Appendix A for details of the neuropsychological testing.

9 Sample Size

For this feasibility study, there are no hypothesis tests and therefore sample size is not based on power. Rather, the sample size of 30 subjects is based on providing a sufficiently robust characterization of adverse events and other study endpoints. With a sample size of 30 subjects, adverse events that have a 5% probability per-subject have approximately an 80% chance of being observed in at least one subject in the study. Study results obtained from a sample of 30 subjects will permit planning for the potential range of results that could occur in a larger pivotal trial.

Up to 45 subjects will be enrolled at up to 8 sites in the United States to ensure that approximately 30 subjects undergo the LITT procedure. It is expected that each site will enroll no more than 10 subjects to ensure that all sites have an opportunity to contribute data to the study and to prevent any one site from having an outsized influence on the overall results of the study.

10 Analysis Populations

The following analysis populations are defined:

- **Enrolled Set:** All subjects enrolled in the study
- **Treated Set:** All subjects that received thermal delivery with the NBS
- **Per-protocol Set:** A subset of the Treated Set that does not have a protocol deviation (see below)

In the feasibility study setting, conclusions about performance are best informed by analyses of the Treated Set. Analyses may be repeated on the Enrolled Set for full reporting of study results and on the Per-protocol Set to provide insight into the potential impact of protocol deviations on the analysis results.

The Per-protocol Set will exclude subjects with protocol deviations that seriously affect the integrity of the data. The deviations that will result in subject data being excluded from the Per-Protocol Set are:

1. Subject did not meet the following study inclusion criteria:

- Diagnosis of unilateral medial temporal lobe epilepsy (MTLE) confirmed clinically and with either (1) ictal scalp recording and MRI evidence of mesial temporal sclerosis or (2) intracranial ictal onset consistent with hippocampal origin.
- Subject or legally authorized representative is able to provide appropriate consent to participate.
- Subject averages 3 or more complex partial seizures (with or without secondary generalization) per month over the 3 most recent consecutive months prior to baseline.

2. Subject should not have undergone the study procedure (i.e. subject was found not to have met the treatment eligibility criteria in Section 6.4 of the clinical study protocol)

Protocol deviations may be reviewed prior to performing analysis of study outcomes to identify deviations, in addition to those identified above, that may result in excluding a subject from the per-protocol set. Reviewing protocol deviations prior to analysis of outcomes is intended to prevent bias in the analysis results while still allowing for identification of significant protocol deviations that could impact outcomes but that were not anticipated at the time that the Statistical Analysis Plan was written.

The reasons that Treated Set subjects are excluded from the Per-protocol Set will be tabulated.

11 Statistical Analyses

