10.2.2 Analysis Populations

All subjects enrolled in the study (including those withdrawn from the investigation) will be accounted for and documented.

The following analysis populations are defined:

Enrolled Set: All subjects enrolled in the study

Treated Set: All subjects that initiate treatment with LITT (received thermal delivery with the NBS)

Per-protocol Set: All subjects in the Treated Set that are treated according to the protocol requirements and meet study and treatment eligibility criteria

In the feasibility study setting, conclusions about performance are best informed by analyses of the Treated Set. Analyses may be repeated on the Enrolled Set for full reporting of study results and on the Per-protocol Set to provide insight into the potential impact of protocol deviations on the analysis results.

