12.2 Disposition of Subjects

All subjects that sign the informed consent form (ICF) will be accounted for by reporting

1. Number of subjects that sign the ICF/enroll
2. Number of subjects that enroll and meet all eligibility criteria
3. Number of subjects that are eligible for treatment (complete the Baseline Phase and meet the treatment criteria)
4. Number of subjects that exit the study prior to LITT treatment
5. Number of subjects that undergo LITT treatment
6. Number of subjects that complete each follow-up visit
7. Number of subjects that exit the study after LITT treatment but prior to the Month 24 visit.

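### The SAP supplied is written to protocol Rev A and does not match Rev B: its Per-protocol exclusion list, part of its seizure baseline, its Baseline adverse event phase and its Week -12/-4 anchors all need aligning

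*SAP*

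**What the plan says.** **Versions.** SAP 3 lists "Monteris FLARE Clinical Study Protocol, Rev A" as its governing protocol. SAP 2 adds: "Changes to the versions of the Clinical Study Protocol (protocol) and Case Report Forms (CRFs) cited above may necessitate updates to the SAP".

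**Per-protocol Set.** SAP 10 defines the set as "A subset of the Treated Set that does not have a protocol deviation (see below"), then lists the deviations that lead to exclusion. One is failing the criterion "Subject averages 3 or more complex partial seizures (with or without secondary generalization) per month over the 3 most recent consecutive months" prior to baseline. Another is failing the "treatment eligibility criteria in Section 6.4 of the clinical study protocol". SAP 10 closes with "The reasons that Treated Set subjects are excluded from the Per-protocol Set will be tabulated". Protocol 10.2.2 defines the set as treated subjects who are "treated according to the protocol requirements and meet study and treatment eligibility criteria". SAP 12.2 item 3 counts the "Number of subjects that are eligible for treatment (complete the Baseline Phase and meet the treatment criteria").

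**Entry rule in Rev B.** Inclusion criterion 3 (6.3.1) requires an average of at least one qualifying seizure per month over 12 months, spelled out as at least 12 in 12 months. Protocol 7.6.1 and Appendix B say instead that 3 months of data determine eligibility.

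**Seizure baseline.** SAP Table 1 dispenses and collects diaries at Weeks -12, -8, -4 and 0. SAP 11.1.3 measures responders against a 3-month Baseline Phase, prorates recorded baseline days to 84, and calculates a longest seizure-free interval for the baseline period. In Rev B the Baseline visit gives diary training only, the diary begins the day after discharge, and earlier seizure data are retrospective, with a subject diary used if one exists (7.6.1, Appendix B).

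**Adverse events and anchors.** SAP 11.1.1 tabulates a Baseline phase before the procedure. Protocol 9.1 and 9.2 collect adverse events from the procedure day. SAP 18.1 and SAP Appendix A use Week -12 or Week -4 visits.

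**The concern.** A per-protocol analysis should show what happens when subjects with deviations are removed. If the SAP list is followed literally for Rev B subjects, it also removes those with lower seizure frequency. The contrast with the Treated Set then mixes deviations with disease severity, and the exclusion table names subjects who have no deviation. If the list is read in the light of its introductory wording, those subjects stay in. Two analysts could therefore build different sets from the same data.

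On the seizure side, two baseline quantities need day-by-day records that Rev B does not require, and the responder reference window differs between the documents. If these choices are left until analysis, they may be made after outcomes are known, which is what SAP 1 says the plan exists to prevent.

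In the safety tables, a Baseline row that is empty because nothing was collected could be read as no events observed.

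**Working it through.** **1. The plan's own figure.** The sample-size statement gives about an 80% chance of seeing a 5% event at least once in 30 subjects. 1 − 0.95^30 = 0.785, which agrees. This point does not depend on it.

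**2. The two thresholds.**
- SAP 10: 3 per month × 3 months = at least 9 in the last 3 months.
- Rev B criterion 3: at least 12 in 12 months, an average of 12/4 = 3 per 3 months.
- Ratio: 9/3 = 3. A subject with a steady rate from 1 to just under 3 per month meets criterion 3 and fails the SAP item. Rev B states no three-per-month threshold anywhere, whichever eligibility window is kept.

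**3. Who falls between them (illustration; the documents give no seizure-rate distribution).**

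*Fixed yearly count.* Assume a subject's n seizures fall at random over 12 months. The chance of fewer than 9 in the last 3 is P(Bin(n, 0.25) ≤ 8).

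| n in 12 months | 12 | 18 | 24 | 36 | 48 |
|---|---|---|---|---|---|
| Chance of failing the SAP item | 99.96% | 98.1% | 87.9% | 43.6% | 11.9% |

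*Fixed underlying rate r per month.* Poisson: P(Poisson(3r) ≤ 8). Clustered: negative binomial with mean 3r and an assumed shape of 2.

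| r | 1 | 2 | 3 | 4 |
|---|---|---|---|---|
| Poisson | 99.6% | 84.7% | 45.6% | 15.5% |
| Negative binomial | 95.4% | 75.6% | 56.7% | 42.9% |

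**4. Why this does not become a head count.** Assume lognormal rates across subjects (log-SD 0.8 to 1.0), Poisson counts in each quarter, eligibility at 12 or more in the year, and exclusion at fewer than 9 in the last quarter. Simulation of 1,000,000 subjects per scenario gives an excluded share of 69–78% if the median rate is 1 per month and 2–5% if it is 16. The assumed median decides the answer.

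**5. The second exclusion.** Section 6 of Rev B ends at 6.3.2 and Section 7 follows. Rev B lists no treatment eligibility criteria, although protocol 10.2.2 still refers to them.

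**6. What each seizure baseline needs, against what Rev B collects.**

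| Quantity | Needs | Rev B retrospective counts enough? |
|---|---|---|
| Rate change and relative change (SAP 11.1.3) | Count and time before treatment | Yes |
| ILAE baseline seizure days (SAP Appendix B) | Seizure-day frequency over the 12 months before surgery | Can serve |
| Responder (SAP 11.1.3) | Baseline count over a named window | Yes, once a window is named: the SAP says 3 months, protocol 10.1.3 says only baseline |
| Seizure-free days, change from baseline | Day-level baseline record | No, unless the subject kept a diary |
| Longest seizure-free interval at baseline | Day-level baseline record | No, unless the subject kept a diary |

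Protocol 10.1.3 itself plans seizure-free days for follow-up only, with no baseline comparison.

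**7. Adverse events and visits.** Because Rev B starts collection on the procedure day, the SAP's Baseline phase has no collection period behind it. The Week -12 and Week -4 visits do not exist in Rev B.

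**The case against.** **This is version control.** The SAP predates Rev B, anticipated an update, and a later SAP may exist. That is correct, and a reader should not infer that the sponsor never updated it; the point applies to the SAP supplied. SAP 20 lets deviations be documented in the study report, which would record the mismatch without settling the choices in advance.

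**The exclusion needs a strained reading.** SAP 10 speaks of protocol deviations and unmet study inclusion criteria, and a subject who satisfies Rev B criterion 3 has neither. This is the best rebuttal, and it shows that the intent was sound. But SAP 10 names the three-per-month item as one of the deviations that lead to exclusion, and its further deviation review only looks for additional exclusions, so nothing in the SAP removes the item.

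**Stronger readings that the documents do not support.**
- *All seizure baseline comparisons fail.* They do not: rate change, relative change and the ILAE baseline need no prospective Baseline Phase diary.
- *A planned comparison is impossible for most subjects.* The share with a pre-procedure diary is not given. The baseline longest interval is to be calculated, but describing its change is optional.
- *A stated fraction of the 30 treated subjects would be lost.* No rate distribution is given, and it is not known whether anyone enrolled under Rev A.
- *The primary safety endpoint is unaffected, or is undermined.* Neither is right. One phase of the adverse event tabulation lacks a collection period; the operative and follow-up phases are not touched by this mismatch.

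**Conclusion.** The point holds as a misalignment between the SAP supplied and Rev B, and it should be fixed before outcomes are analysed. One stated exclusion rule, read literally, builds a set that contradicts both the SAP's own definition and protocol 10.2.2. Another points to a section that does not exist. Two baseline measures lack required data, one responder window is unsettled, and one adverse event phase and several visit anchors have no counterpart in Rev B.

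The number of subjects affected cannot be computed. The probabilities shown rest on assumed random or clustered seizure timing. They show only that subjects near the Rev B minimum would almost all fail the SAP item (95–99.96% across the models).

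Consequences are limited. The Treated Set leads; Per-protocol, responder and seizure-free-day analyses are optional; the SAP 18 sensitivity analyses are optional; and the seizure outcomes are secondary and descriptive. The sample size is unaffected.

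**What to change.** Before any outcome analysis:

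1. **SAP 10.** Replace the three-per-month item with: did not meet the seizure-frequency inclusion criterion of the protocol version under which the subject was enrolled. Remove the Section 6.4 and treatment-criteria references in SAP 10, SAP 12.2 item 3 and protocol 10.2.2, or define those criteria.
2. **Baseline window.** Name one retrospective window in both documents for change, relative change and responder. Report how many subjects have incomplete coverage of it.
3. **Day-level measures.** Report seizure-free days and longest seizure-free interval for follow-up. Compare with baseline only in subjects who have day-level pre-procedure data, and state how many there are.
4. **Anchors and adverse events.** For Rev B subjects, replace the Week -12, -4 and 0 anchors with the Baseline visit. Drop the Baseline adverse event phase, or limit it to any subjects enrolled under Rev A.
5. **Eligibility window.** Reconcile protocol 6.3.1 criterion 3 (and its copy in the synopsis) with 7.6.1 and Appendix B. This review does not choose between them.

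The cost is a SAP revision and short wording corrections in the protocol, with no added visits, data collection or subjects. The real loss is that baseline comparisons of the two day-level measures rest on fewer subjects.
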